The PASI has been developed to provide quantitative assessment of psoriasis lesional burden based on the amount of BSA involved and degree of severity of erythema, induration, and scale, weighted by body part. The head, upper extremities, lower extremities, and trunk are assessed separately and then combined using weighting based on the surface area represented by each area (head 0.1, upper extremities 0.2, trunk 0.3, and lower extremities 0.4). The degree of erythema, induration, and scale in each area is judged on a 0–4 scale, the sum of which represents disease severity. The area of involvement of each area is graded from 0–6, depending on the estimated percentage of lesion area (0: 0 %, 1: 0-10%, 2: 10-29%, 3: 30-49%, 4: 50-69%, 5: 70-89%, and 6: 90-100%). These body scores are multiplied by the disease severity score and the weighting for each body area, yielding a score between 0 and 72^{10} .

Harvey-Bradshaw Index (HBI):

The Harvey-Bradshaw index is a score for quantification of symptoms in patients with CD. It consists of only clinical parameters:

general well-being (0 = very well, 1 = slightly below average, 2 = poor, 3 = very poor, 4 = terrible)

_ 14

Confidential Information

No use or disclosure outside AbbVie is permitted without prior written authorization from AbbVie

abdominal pain (0 = none, 1 = mild, 2 = moderate, 3 = severe) number of liquid stools per day abdominal mass (0 = none, 1 = dubious, 2 = definite, 3 = tender) complications, as above, with one point for each.

The values can range from 0 (in healthy subjects) to 30 points, whereas moderate to severe patients have Harvey-Bradshaw index \geq 7. A score of less than 5 is generally considered to represent clinical remission¹².

Partial Mayo score (PMS)

For the evaluation of the patient's disease activity the partial Mayo score will be documented at each visit. In this study, an average score of five measurements (see subscore sections) shall be used for analysis. The partial Mayo Score has been proven to be a valid and reliable noninvasive measure to evaluate disease activity in adults with UC¹³. If endoscopy is routinely performed during the visit the full mayo score can be documented¹⁴. (Please see definition of Mayo Score below)

The Mayo Score is a composite of the following subscores: Stool Frequency subscore, Rectal Bleeding subscore, Endoscopy subscore, and Physician's Global Assessment subscore¹³.

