The Partial Mayo Score is a composite of the following subscores: Stool Frequency subscore, Rectal Bleeding subscore, and Physician's Global Assessment subscore¹⁴.

Stool Frequency Subscore

The stool frequency subscore is calculated by comparing the stool frequency to a reference number. The reference number is the number of stools per day (24 hours) that is typical for the subject when having active UC but not experiencing a flare and needs to be designated once prior to enrollment. The reference number should represent a full number of at least 1.

Subjects will record the daily number of stools throughout the trial. Using these numbers, the Stool Frequency subscore will be assessed for each study day as follows:

A number of bowel movements lower than or equal to the reference number of bowel movements should be scored as 0 = Normal.

Confidential Information

One or 2 bowel movements more than the reference number of bowel movements should be scored as 1.

Three or 4 bowel movements more than the reference number of bowel movements should be scored as 2.

Five or more bowel movements more than the reference number of bowel movements should be scored as 3.

The Stool Frequency subscores from the 5 days prior to each study visit will be averaged and used for the Stool Frequency subscore for each study visit.

The Stool Frequency subscore during days which the subject received anti-diarrheal medication will be scored as a 3.

Diary entries for stool frequency should not be included in the 5 days prior to the visit that are evaluated for the Stool Frequency subscore for the following days: (1) the day the subject received medication for bowel preparation prior to endoscopy, (2) the day the subject underwent an endoscopy, and (3) 2 days following the endoscopy. Earlier diary entries will be used accordingly in order to provide the most recent data for 5 days prior to the respective study visit.

Rectal Bleeding Subscore

Subjects should record a daily rectal bleeding subscore value as follows:

No visible blood with stool during the respective day should be scored as 0.

Visible blood with stool less than half the time during the respective day should be scored as 1.

Visible blood with stool at least half the time during the respective day should be scored as 2.

A score of 3 for bleeding requires subjects to have at least 50% of bowel movements accompanied by visible blood and at least one bowel movement with blood alone.

_ 16

Confidential Information

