The PASI score for each body region is obtained by multiplying the sum of the severity scores by the area score, then multiplying the result by the constant weighted value assigned to that body region. Since the head, upper extremities, trunk, and lower extremities correspond to approximately 10, 20, 30, and 40% of body surface area, respectively; the PASI score is calculated using the formula

$$PASI = 0.1(E_h + I_h + D_h)A_h + 0.2(E_u + I_u + D_u)A_u + 0.3(E_t + I_t + D_t)A_t + 0.4(E_l + I_l + D_t)A_l$$

where E, I, D, and A denote erythema, inducation, desquamation, and area, respectively, and h, u, t, and l denote head, upper extremities, trunk, and lower extremities, respectively. PASI scores range from 0.0 to 72.0 with the highest score representing complete erythroderma of the severest degree.

Based on articles: Fredriksson T, Pettersson U. Severe psoriasis--oral therapy with a new retinoid. Dermatologica. 1978;157(4):238-44, and Mease, P. J. Measures of Psoriatic Arthritis. Arthritis Care Res, 2011,63(Suppl 11): S64–S85.

Harvey-Bradshaw Index (HBI)

HBI BASED ON PATIENT'S SYMPTOMS IN PREVIOUS 24 HOURS

General Well-Being

0 = very well, 1 = slightly below par, 2 = poor, 3 = very poor, 4 = terrible

Abdominal Pain

0 =none, 1 =mild, 2 =moderate, 3 =severe

Number of Liquid Stools per Day

Abdominal Mass

0 =none, 1 =dubious, 2 =definite, 3 =definite and tender

92

Confidential Information

Complications: (Score 1 Per Item)	
Arthralgia	
Uveitis	
Erythema Nodosum	
Aphthous Ulcers	
Pyoderma Gangrenosum	
Anal Fissure	
New Fistula	
Abscess	

Harvey-Bradshaw Index Score:

<5	remission
5 – 7	mild
8-16	moderate
>16	severe

Based on the article Harvey RF, Bradshaw JM. A simple Index of Crohn's disease activity. Lancet 1980; 1:514.

Partial Mayo score (PMS)

Based on Patients symptoms in previous 24 hours	Score	
Stool Frequency		
0 = normal,		
1 = 1 to 2 stools per day more than normal	3 6 - 1 33	
2 = 3 to 4 stools per day more than normal		
$3 = \ge 5$ stools per day more than normal		
Rectal Bleeding		
0 = No Blood seen		
1 = Streaks of blood with stool less than half the time	8 	
2 = Obvious blood with stool most of the time		
3 = Blood alone passes		
	93	

Confidential Information

abbvie	Adalimumab P13-562 Protocol	
Physician's Glo	bal Assessment	
0 = Normal		
1 = mild disease	9	
2 = moderate di	sease	
3 = severe disea	ise	
	3-4 mild; 5-6 moderate; \geq 7 severe TOTAL	
Was Endoscopy	γ performed in this Visit? \Box yes \Box no	
If Yes:		

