Endoscopic find	lings	
	lings	
Endoscopic find		
Endoscopic find 0 = Normal	e	
Endoscopic find 0 = Normal 1 = mild disease	e sease	·
Endoscopic find 0 = Normal 1 = mild disease 2 = moderate di	e sease	
Endoscopic find 0 = Normal 1 = mild disease 2 = moderate di 3 = severe disea	e sease	partial
Endoscopic find 0 = Normal 1 = mild disease 2 = moderate dia $3 = severe disease\leq 2 no activity;Mayo Score)$	e sease ise	partial

Full Mayo Score (FMS) is obtained when the endoscopy has been performed and the score of the endoscopic finding has been added to the partial Mayo score.

_ 94

HUMIRA®

(Adalimumab)

complete at visit 1 and entry changes as appropriate at each visit

Concomitant Medication, Other Medication And Supplements:

1. Name (Trade name preferred)	2. Start date	3. End date
	_ _ _ _ _ _ _ DD MON YY	_ _ _ _ _ _ DD MON YY
4. Dose and Units and Route of Administration	5. Frequency	6. Reason for use
	□ 1qd □ 2bid □ 3tid □ 4qid	
	Other:	
1. Name (Trade name preferred)	2. Start date	3. End date
	_ _ _ _ _ _ DD MON YY	_ _ _ _ _ _ _ DD MON YY
4. Dose and Units and Route of Administration	5. Frequency	6. Reason for use
	□ 1qd □ 2bid □ 3tid □ 4qid	
	Other:	

Visit 1 (=screening)

_ 95

Confidential Information No use or disclosure outside AbbVie is permitted without prior written authorization from AbbVie

1. Name (Trade name preferred)	2. Start date	3. End date
	_ _ _ _ _ _ _ DD MON YY	_ _ _ _ _ _ _ DD MON YY
4. Dose and Units and Route of Administration	5. Frequency	6. Reason for use
	□ 1qd □ 2bid □ 3tid □ 4qid	
	Other:	
1. Name (Trade name preferred)	2. Start date	3. End date
	_ _ _ _ _ _ _ DD MON YY	_ _ _ _ _ _ DD MON YY
4. Dose and Units and Route of Administration	5. Frequency	6. Reason for use
	□ 1qd □ 2bid □ 3tid □ 4qid	
	Other:	

96

HUMIRA[®]

(Adalimumab)

complete at visit 1 and entry changes as appropriate at each visit

Concomitant Medication, Other Medication And Supplements:

If there is a change in medication fromVisit 1 please specify below. The change has been carried out on :_____(DD/MM/YY)

1. Name (Trade name preferred)	2. Start date	3. End date
	_ _ _ _ _ _ DD MON YY	_ _ _ _ _ _ _ DD MON YY
4. Dose and Units and Route of Administration	5. Frequency	6. Reason for use
	□ 1qd □ 2bid □ 3tid □ 4qid	
	Other:	
	ould.	
1. Name (Trade name preferred)	2. Start date	3. End date
	_ _ _ _ _ _ DD MON YY	_ _ _ _ _ _ _ DD MON YY
4. Dose and Units and Route of Administration	5. Frequency	6. Reason for use
	□ 1qd □ 2bid □ 3tid □ 4qid	

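### The Partial Mayo form's 24-hour look-back contradicts Section 6.5.1 (5-day average, endoscopy days excluded); a site following the form at an endoscopy visit can add up to 3 of 9 points

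*Combined protocol and SAP*

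**What the plan says.** Section 6.5.1 (Description of Activities, Partial Mayo score) has the PMS documented at every visit and says that an average of five measurements goes into the analysis. For stool frequency, "The Stool Frequency subscores from the 5 days prior to each study visit will be averaged"; the rectal-bleeding entries are averaged over the same 5 days. Three kinds of day are left out of both subscores: "the day the subject received medication for bowel preparation prior to endoscopy", the endoscopy day, and the 2 days after it. The gap is filled from further back: "Earlier diary entries will be used accordingly in order to provide the most recent data for 5 days prior" to the visit. Endoscopy is optional: "If endoscopy is routinely performed during the visit the full mayo score can be documented".

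The PMS page in Appendix D is headed with a look-back of 24 hours and takes one value per subscore. Below the total it asks whether endoscopy was performed at this visit. It then states that "Full Mayo Score (FMS) is obtained when the endoscopy has been performed and the score of the endoscopic finding has been added" to the partial score. The page has no 5-day average, no excluded or replacement day, and no pointer to Section 6.5.1.

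Change in PMS in UC patients is a secondary objective (Section 5.2) and a secondary endpoint at Visits 2 to 5 (Section 11.1.2).

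**The concern.** The authors recognised that bowel preparation and endoscopy disturb stool counts and bleeding, and wrote a rule against it. The form on which the score is entered does not carry that rule, and its shorter window makes the conflict sharpest at endoscopy visits. The difference in window and averaging applies at every UC visit. The missing exclusion matters only where an endoscopy falls close to the visit.

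At stake is the PMS change. A contaminated Visit 1 value exaggerates later improvement; a contaminated later value hides improvement or looks like a flare. Little in the plan would catch this. Section 9.0 says the study is not monitored and that entries are checked for consistency, and a raised stool subscore is internally consistent. Section 6.5.1 relies on a daily diary, but neither the schedule of activities nor the legible part of Appendix D shows one.

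**Working it through.** The plan states no figure to reproduce: Section 11.2 describes a descriptive study without a hypothesis. The check sets the two texts side by side and then scores the same patient under each rule.

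**Step 1: which days are eligible.** Let the endoscopy visit be day 0 and assume that preparation falls on day −1.
- Form: the previous 24 hours, which lie on days −1 and 0.
- Section 6.5.1: days −1, 0, +1 and +2 are excluded, and the 5 most recent earlier days are used.
- The form's window then contains no eligible day.

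**Step 2: score the stool subscore.** Both texts use the same cut-points for stools above the patient's reference: none gives 0, 1–2 gives 1, 3–4 gives 2, 5 or more gives 3. Write s(x) for this function, b for the patient's usual extra stools and p for the extra stools due to preparation. The values of b and p are assumptions.
- Form: s(b + p)
- 5-day mean without the exclusion: [4·s(b) + s(b + p)] / 5
- Section 6.5.1: s(b)

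| b | p | Form | 5-day, no exclusion | Section 6.5.1 | Form excess | 5-day excess |
|---|---|---|---|---|---|---|
| 0 | 1 | 1 | 0.2 | 0 | +1 | +0.2 |
| 0 | 3 | 2 | 0.4 | 0 | +2 | +0.4 |
| 0 | 5 | 3 | 0.6 | 0 | +3 | +0.6 |
| 1 | 1 | 1 | 1.0 | 1 | 0 | 0 |
| 1 | 3 | 2 | 1.2 | 1 | +1 | +0.2 |
| 1 | 5 | 3 | 1.4 | 1 | +2 | +0.4 |
| 2 | 5 | 3 | 1.4 | 1 | +2 | +0.4 |

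A patient whose stool subscore is already 3 gains nothing.

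**Step 3: put it on the scale.** PMS runs to 3 × 3 = 9 and the Full Mayo Score to 4 × 3 = 12. The largest excess through the stool subscore is 3 points on either. On the form's printed bands (2 or less none, 3–4 mild, 5–6 moderate, 7 or more severe), a PMS of 0 becomes 3 (none to mild) and a PMS of 2 becomes 5 (none to moderate). Rectal bleeding and the physician's global assessment, which takes account of both patient-reported subscores, could also move; the documents give no basis for a figure.

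**Step 4: the group mean.** The shift in the UC mean at a visit is f × d, where f is the share of patients with an affected endoscopy visit and d is their average excess. The documents give neither. With f anywhere from 0 to 50% (assumed) and d from 0 to 3, the product runs from 0 to 0.5 × 3 = 1.5 points, which is too wide to serve as an estimate. Section 6.2 plans about 30 patients for the Crohn's disease and UC group together and does not give the UC share.

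**The case against.** The strongest reply is that the rule exists and governs. Section 6.5.1 states it in full, Section 10.0 has data entered according to the protocol, and the source for the two subscores is the diary, not the entry page. A site that applies Section 6.5.1 despite the form's heading makes no error. This stands. A reader might infer that laxative-induced stools do enter the UC score; the documents show only that they can, where a site follows the form. The reply does not remove the contradiction, because a site completing the page as printed departs from Section 6.5.1.

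The large effect also comes mainly from the 24-hour window: over 5 days without the exclusion, the excess in the cases above is at most 0.6. That is correct, and it is why window, averaging and exclusion need reconciling together.

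Three stronger readings are tempting and are not supported.
- **Harvey-Bradshaw Index.** Its form is also headed "HBI BASED ON PATIENT'S SYMPTOMS IN PREVIOUS 24 HOURS" and counts liquid stools. But Section 6.5.1 sets no endoscopy exclusion for that index, so nothing is contradicted.
- **Share of patients reclassified.** Setting the stool subscore to 3 moves 38 of the 48 subscore combinations with a lower stool score (16 + 15 + 7, or 79%) into a worse band. This weights every combination equally and assumes at least 5 extra stools. It is not a proportion of patients.
- **A figure for baseline inflation.** This would need endoscopy rates and true stool scores that are not given. Patients are starting treatment for active disease, so baseline stool scores may be near the ceiling. Endoscopies at baseline and at follow-up also push the change in opposite directions and may partly cancel.

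**Conclusion.** The contradiction holds. Section 6.5.1 and the Appendix D page disagree on the look-back window and averaging at every UC visit. At a visit with endoscopy, the form's window normally contains only days that Section 6.5.1 excludes. This assumes preparation on the day before or the day of the endoscopy. For a single patient the excess through the stool subscore is 0 to 3 points, and the same error passes into the Full Mayo Score. The effect on the UC group mean cannot be determined from the documents.

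The reach is limited: one secondary endpoint in part of a group of about 30, and the optional Full Mayo Score. The primary endpoint, based on the Beliefs about Medicines Questionnaire, is untouched. Some of the eCRF text is broken, so a diary page elsewhere cannot be ruled out, but the PMS page is legible and carries no exclusion. The point should be corrected because the form as printed can yield a value the protocol does not intend, and the remedy is cheap.

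**What to change.** Reconcile the PMS page with Section 6.5.1 on three items together: the look-back window, the 5-day averaging, and the excluded and replacement days. One way is to replace the 24-hour heading with the Section 6.5.1 rule. Adding only an exclusion line would leave the conflict between 24 hours and 5 days in place. State which recorded value is analysed.

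For PMS values recorded on the 24-hour form, flag those with endoscopy marked yes and specify, in the data analysis plan that Section 11.2 promises before analysis, that PMS change is reported with and without them. The flag uses an item already collected. It will miss an endoscopy done a day or two before the visit, because the form asks only about the visit itself, and the report should say so.

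Section 6.4 estimated the end of inclusion as September 2016 and this protocol version is dated 27 October 2016. On that schedule a form change could help only remaining follow-up visits, and baseline values depend on the flagged analysis. The cost is one form edit, a little more analysis, and reliance on a diary or recall for the earlier days.
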